2. PARTICIPANTS

2.1 Describe the general characteristics of the intended primary participant populations, including age range, gender, sexual orientation, racial/ethnic background, socioeconomic status, health status, criminal history, and any other characteristics relevant to the study.

Proposed initial and primary recruitment strategy drawing from the existing WTV member base will produce a sample that is representative of this group but not representative of all CSOs of an IP with an OUP. Many CSOs may have drug or mental health problems themselves, distrust mental health services, or are content being distanced from their problem-wrought IP (Slesnick et al., 2000). These CSOs often do not seek help and they are not the target population for this

study. The target population consists of CSOs who are concerned about their loved one's problems in general and their opioid use in particular, and whose own functioning is not seriously impaired by their own drug use or mental health issues. Also, the sample will be limited to CSOs who have internet access and are willing to receive services from web-based sites. Although this is not representative of all CSOs of individuals with OUP, it is representative of those who would use the services being evaluated.

Gender Representation: In past CRAFT studies, the vast majority (anywhere from 75%-90%) of participants are female. Because women are more likely to seek help (Trudeau et al., 2002), we expect CSOs in this study sample will continue to be predominantly female. Because this is an early stage pilot and feasibility study, we will not conduct targeted recruitment efforts to recruit male CSOs but in the future this would be possible.

Racial/Ethnic Representation: Given the proposed small sample size (up to 84 CSOs) for this pilot and feasibility study, we anticipate that we will not have a sufficient number of minorities in any group to do demographic analysis. Still we expect to have some minority representation in our participants. If we receive an overwhelming response to our recruitment efforts, if eligible, we will over include individuals in those groups to increase representation. Relative to the racial demographics in the 2017 Census for the United States (60.7% White, 13.4% Black, 5.8% Asian, 18.1% Hispanic or Latino, 1.3% American Indian or Alaska Native, 0.2% Native Hawaiian Other Pacific Islander), if we were to represent this makeup in our study, we might expect: 27, 6, 2, 8, 1 participants respectively; we'd expect this distribution adjusted for the online over-indexing of white participants.

Socio-economic Representation: Given the study is to be implemented completely online using digital intervention and data collection methods, we expect the sample to skew with CSOs from a higher SES background. Furthermore, inclusion criteria require CSOs to have smart phones with data or computers with internet, which may be a barrier for some people with limited internet/data plans or CSOs who do not have their own smart phone or computer. However, this may not occur given many people across SES levels do have their own smartphones and computers with internet capability.

While the increase in opioid use has increased across diverse groups, white, non-Hispanic adults continue to experience higher rates of opioid use problems and overdose deaths. According to an analysis of National Vital Statistics by the Kaiser Family Foundation, the overall rate of opioid overdose death in 2017 was 14.9 per 100,000 persons in the United States. In 2017, white, non-Hispanic persons had the highest fatal opioid overdose rate (19.4 per 100,000 adults) compared to their black and Hispanic counterparts (12.9 & 6.8 per 100,000 persons, respectively). In addition, the rate of opioid overdose deaths among males is approximately twice as high for males compared to females (20.4 vs. 9.4 per 100,000 persons, respectively). Persons from a lower SES background, including those "living in poverty, being unemployed and having Medicaid," continue to experience opioid use problems and overdose deaths at higher rates compared to their more well-off counterparts (Ghertner & Groves, 2018).

We The Village currently does not collect demographic information from members; however, anecdotal review of their existing membership found the majority were white, female and from a higher SES background. During the pilot study, WTV will collaborate with organizations serving a wider, diverse population, especially communities of color and lower SES backgrounds.

2.2 Select all populations, settings, or records that will be involved in the research. Complete the corresponding appendix for each selection.

- People who use substances, substance use treatment sites, and/or substance use records ([Appendix J](#))
- Students, school settings, and/or student education records ([Appendix L](#))

For protocols that meet the criteria for exempt research, skip to Section 4.

2.3 Select all intended primary participant populations. Complete the corresponding appendix for each selection.

- Pregnant women ([Appendix G](#))
- Prisoners ([Appendix H](#))
- Children ([Appendix I](#))
- People with limited decision-making capacity ([Appendix K](#))

2.4 List the study inclusion criteria.

1. Identify as a concerned significant other (CSO) of a loved one with an OUP
2. Be 19 years or older
3. No substance use disorder
4. Has concern about the opioid use of a loved one (IP)
5. Plans to be in close contact (phone/face-to-face) with the IP
6. The IP is not currently receiving treatment, or the IP is in treatment, but the CSO perceives the IP may benefit from additional treatment (e.g., receiving MAT but the IP may benefit from attending outpatient services, or in residential treatment, but will need to enter outpatient treatment upon discharge).

2.5 List the study exclusion criteria.

1. Does not agree to sign the consent form
2. Is not English-speaking
3. Is not able to understand the consent form
 - a. Pass a multiple choice consent quiz (i.e., 100% correct responses) that tests the participant's comprehension of basic elements of informed consent and the requirements of the protocol administered by the research team over the phone.
 - b. Participants will be given up to three opportunities to pass the consent quiz
4. Does not have personal access to a smart phone with data or a computer with internet to be able to access the digital platform for the study conditions, quizzes, questionnaires, and follow-up communication
5. Reports that they have a drug abuse problem or a history of drug abuse or dependence and that they have not been in recovery for at least 2 years
6. Resides outside the United States

2.6 Provide justification for the exclusion of broad population groups.

The study design excludes anyone under 19 years old. The primary hypothesis for the study is to help CSOs increase treatment utilization among IPs. Children are typically not the CSO who is responsible for treatment decisions of the IP with an OUP.

While the adult population may include persons age 18 years old, the proposed study is excluding potential 18-year-old participants because they may still be in high school and not the primary CSO to support treatment decisions.

3 RECRUITMENT AND SCREENING

3.1 Identify the expected number of individuals screened and the expected number of individuals consented/enrolled to reach your target sample size. If multi-site, break the total down per study site. If multi-year, break the total down per study year.

For this pilot and feasibility study we plan to enroll up to 84 CSOs

3.2 Describe how prospective participants will be identified and recruited. Include information about: how, when, where, and by whom (by position or role, not by name). Describe any recruitment materials that will be used to recruit prospective participants.

As shown in Figure A, we will conduct outreach using multiple recruitment methods. We expect the majority of participants may be recruited from the existing 1,500 WTV member base, who currently engage in We The Village's peer support online forum; however, we will also utilize personal WTV member referrals, social media platforms, print media, and referrals from partner organizations. Currently, WTV's social network outreach could potentially reach 15,000 persons. WTV team (PI, coaches, and staff) will post recruitment ads and flyers on the WTV website and forum, as well as on other social media platforms. In addition, we will develop partnerships with providers, who serve diverse populations, including communities of color and lower SES. The JoinGroups.Com organization goes into underserved rural areas and establishes a health center to address medical and behavioral health needs, including in-person support groups for people with substance use problems. The Sixth Street Community Center serves a Latinx population. We will post recruitment advertisements on professional counseling member boards, such as the Association of Black Social Workers. All recruitment materials will direct interested individuals to the study page, so they can learn more about the study and complete an anonymous screening survey. We will not collect any identifying information during the screening process. If someone starts the screening survey but does not finish it, we will not be able to reach out to them and they will not be included in the screened category. We will track the number of incomplete screenings throughout the pilot study and where in the screening survey do people drop off. If they screen eligible, they will be directed to click the consent form link. If they screen ineligible, they will be directed to click a link to learn more about WTV and joining the business as usual peer support online forum. They will also be provided the study number if they have any questions and want to speak to a study staff person. If someone calls into the study to be screened over the phone, we will answer any questions, then refer them to the link located on the study's landing page to complete screening and the consent form.

[figure not shown]
After completing informed consent, participants will be asked to call the research study phone number to complete a consent quiz and to confirm enrollment. They will have the option of calling the number to speak with a study staff person or completing an online request contact form. The brief contact form will ask for a participant's phone number and email address and best time period to contact them. The goal is to speak with participants within one business day after completing informed consent. These calls will be completed by study staff, including the research assistant, senior project manager, and intervention staff, if needed. During the

confirmation call, study staff will administer the brief consent quiz and provide information on next steps, if the participant answers 100% of the questions correct. If the person does not answer 100% of the questions correctly, the study staff person will review the consent form with the participant and re-administer the consent quiz. Participants will have up to three times to pass the consent quiz. If they do not pass the third time, they will be informed that they are not eligible for the study.

After administering the consent quiz during the confirmation call, study staff will answer questions, review next steps, and clarify expectations. If a potential participant did not pass the consent quiz, study staff will be able to review the appropriate consent form sections and to re-administer the consent quiz. After completing the confirmation call, all eligible study participants will be considered enrolled into the study. Study staff will send via email secure Survey Gizmo links with the HIPAA authorization form, locator form and baseline survey. The HIPAA authorization form will now have an option for "I'm not sure." If someone selects the not sure option, they will be directed to call the study number to discuss their concerns or ask questions before moving forward in the enrollment process. Participants must agree to the HIPAA authorization to continue with the study. After agreeing to the HIPAA authorization, participants will click the next step link to complete the locator form. After completing the locator form, participants will click a link to complete the baseline survey. The brief locator form will request important contact information in order to locate participants for the follow-up survey and to re-engage with research and intervention activities, if needed. For participants who report they share their email address with someone else, we will ask them if they are sure it is okay for us to send information to this email address. If they say No or Prefer not to answer, they will be asked if they have a secondary email address they want to use. If someone does not complete the locator form or baseline survey, study staff will reach out to the participants to encourage them to complete these required activities. All participants will have one week to complete the enrollment process. Randomization will occur after completing the baseline survey. We will use block randomization to assign a group of three participants to each condition. We will wait till we have at least people randomized to Program A to begin the program. Participants will be informed of their assigned group after completing their baseline survey. WTV will notify participants of their randomly assigned program and the appropriate next steps for their specific program assignment. This change will allow us to conduct block random assignment computed by [name] and to allow us to equal number of people in each group throughout the study recruitment period. We will program Survey Gizmo to send the research team an automatic email when someone completes the baseline survey.

When Program A reaches approximately nine participants, we will form the next group assigned to Program A. We will follow-up participants who have incomplete digital data collection that occurs after consent for up to two times.

Figure A: Recruitment and Enrollment Flowchart

Recruitment activities will be conducted after IRB approval through March 31, 2020 or until we recruit up to 84 eligible CSOs, whichever comes first. We will track and document which recruitment strategies yield the best engagement. Please see examples of images and messaging we will use for different methods of recruitment. We plan to implement the following recruitment methods:

a. Recruitment channels

i. Participants will be recruited through the following methods as needed:

1. WTV Promotions (e.g., website callouts, emails, social media posts and 1:1 message) to existing and future WTV members.
2. Engagement of the membership group to suggest a friend and make a referral if they know anyone who fits the participant description.
3. Reaching out to existing partners who provide services to patients with OUD.
 - a. Sixth Street Community Center
 - b. Tempest
 - c. Rebel For A Change
 - d. Best Day Ever
 - e. Center for Motivation and Change

- f. JoinGroups.Com (medication-assisted treatment (MAT) for opioid addiction)
- 4. Develop recruitment strategies to increase diversification of study participants
 - a. Promote research study on the following professional counseling member websites:
 - i. Association of Black Psychologists (ABPsi)
 - ii. National Association of Black Social Workers (NABSW)
 - b. Develop new partnerships with providers who serve more diverse populations, including communities of color and lower SES
- 5. Targeted digital and local advertising efforts.
 - a. Facebook
 - b. Instagram
 - c. Google

3.3 Describe how prospective participants will be screened. Include information about: how, when, where, and by whom (by position or role, not by name). Describe any instruments that will be used or tests that will be performed during the screening process.

As discussed above, we plan to utilize wide-ranging requirement strategies to reach our target sample size. While WTV is located in New York City, participants may live across the United States. When a prospective participant responds to a recruitment message, flyer or referral, they will be directed to visit the We The Village Family Support study webpage. On the study website, prospective participants will have the opportunity to read a description of the study, including goals and expectations. If individuals are still interested, they will be directed to click the Screening Survey link. The link will take them directly to the start of the Screening Survey. The Screening Survey is a self-administered multiple choice online SurveyGizmo tool.

We will program automated scoring to inform participants immediately after filling out the screening survey if they are eligible, unless their answers are not clearly eligible or ineligible, such as reporting “other type of drug used by their loved one.” If the results of their screening survey are indeterminate, they will receive a message to call the study number to speak with a study staff person.

3.4 Describe the information you will obtain for screening. Explain whether you will retain this as part of the study data.

We will retain all the information we received as part of the screening process. During the screening process, we will collect information on prospective participant’s year of birth, US residency, access to a computer or smart phone, their own substance use disorder diagnosis, type of relationship with IP, frequency of face-to-face interactions with their IP, perceptions of their IP’s opioid use, IP’s symptoms of opioid use or misuse, the types of substances used by IP, current treatment plan for their IP, and their ability to commit the time and resources to the study. All screening data will be de-identified and will not be connected to any future data collection activities.

3.5 Describe how screen failures will be handled and, if applicable, describe the conditions and criteria upon which re-screening is acceptable.

[figure not shown]
A study phone number and email address will be listed on the study landing page for prospective participants if they experience technical difficulties or have questions. If a prospective participant's answers do not make them clearly eligible or ineligible, they will be encouraged to call, or email the study team, most likely the Research Assistant, for additional information. We will attempt to communicate with participants within one business day. The Research Assistant will re-screen participants without collecting any identifying information to determine eligibility. If the person is eligible, they will be re-directed to the study landing page to complete the informed consent process and re-enter the digital enrollment flow. This procedure will improve screening rates and minimize potential eligible participants screening out of the study. If the person is not eligible, study staff will inform the person and ask them if they are interested in learning more about the We The Village community.

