4 STUDY PROCEDURES

4.1 Provide a detailed description of the study procedures in chronological order. As applicable, include information on: differences between the control and experimental groups, the number of follow-up visits, study visit windows, participant time commitment per activity, and the setting/location per activity.

Study procedures are outlined in the figure below. After screening eligible participants complete online enrollment, which includes providing informed consent, passing a consent quiz during the confirmation call by study staff (research assistant), agreeing to the HIPAA authorization form, and completion of the locator form and baseline survey. Participants are then randomized into one of three groups.

Participants assigned to the PEER group (Program C) will participate in an online peer support forum with other CSOs. Members of the forum post questions or comments to weekly peer-led discussions and receive responses and feedback from other CSO forum members. Members typically express concerns regarding their IP's wellbeing and ask other members to share any strategies they have employed when dealing with their IPs.

Interactions typically, are based either in 12-Step strategies members have learned (usually through Al-Anon or Nar-Anon Family Groups or Family Training Workshops provided by treatment programs) or in CRAFT skills learned (usually from treatment programs or other We The Village members). A staff member from We The Village monitors forum interactions to ensure members are interacting respectfully. This individual also will report any adverse or severe adverse events that members mention online.

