Participant assigned to the CRAFT-A (Program A) and CRAFT-C (Program B) groups will have access to a 12-module on-line CRAFT intervention and asked to complete one module weekly for 12 weeks. Modules introduce CRAFT concepts and provide workbooks to assist participants in learning and applying the concepts. The modules include: 1) Introduction to CRAFT; 2) Communication Training; 3) Functional Analysis of Drug Using; 4) Positive Reinforcement; 5) Withdrawing Reinforcement; 6) Allowing Natural Consequences; 7) Problem-solving; 8) Life Enrichment; 9) Suggesting Treatment; 10) Recovery and Relapse; 11) Relationship; and 12) Recap of Skills. CRAFT-A participants also attend a weekly 60-minute online group sessions facilitated by a CRAFT-certified coach. CRAFT-C participants attend a weekly 60-minute individualized on-on-one coaching session with a CRAFT-certified coach. During weekly group or individual sessions concepts are briefly reviewed, questions are answered, and skills are practiced through role-plays of common situations. One-on-one sessions involve role-plays that are tailored to the participants' specific circumstances.

Counselors must complete their CRAFT training and certification prior to implementing Program A and Program B. In addition, CRAFT counselors must complete CITI training as limited personnel.

STUDY ACTIVITIES BY PROGRAM		
Experimental Programs		Standard Care Program
Program A & Program B		Program C
● Commit 1½ to 1¾ hours a week	● Commit 1 to 1½ hours a week	
● Watch a 12-module online support program delivered weekly	● Join a private online support forum for people with a loved one with an opioid use problem	
● Each module will be 30 to 45 minutes in length	● Gain access to knowledge and experiences of fellow CSOs shared in peer-led forum discussions	
● Attend weekly 60-minute online sessions facilitated by a CRAFT coach via Zoom or phone	● Post your own questions specific to your current situation and receive support from peers and WTV moderators	
● Review content from the weekly module	● Share your knowledge and experience to answer fellow CSOs' questions and to support others through their journey	
● Participate in a Question and Answer segment		
● Practice content with role-plays		
Program A		Program C
● Weekly sessions are in a small group with WTV coach and 3 to 8 study participants using Zoom	● Weekly sessions are one-to-one with WTV coach using Zoom	● Discussions are self-initiated and ongoing

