8 PRIVACY AND CONFIDENTIALITY

8.1 Describe procedures to protect participants' privacy during the study (i.e., precautions you have taken to protect the participant from being recognized as a research subject).

- Participants will be assigned an identification number which will be affixed to all collected data. Linkage between participant identity and identification numbers will be stored in a password protected electronic file on a secure network drive at Public Health Management Corporation accessible by key study staff.
- Participant enrollment spreadsheet will be password-protected and sent to WTV via encrypted email. WTV will be responsible for contacting enrolled participants to inform them of their random assignment, to discuss next steps, and to provide \$20.00 gift card incentive payment for completing a survey. This file will not be connected to study data.
- Data collected as part of the online intervention activities will also be kept confidential. Participants will be instructed to create a unique username that does not use their last name or email address.
- When contacting participants for study-related purposes, staff will follow a locating and contact protocol that will decrease the chances someone will be identified as a research subject.

8.2 Describe all of the procedures you will use to protect participants' confidentiality during the study (i.e., precautions you have taken to protect participants' data from being unnecessarily and inappropriately disclosed; e.g., authorization of access, password protection, encryption, physical controls, certificates of confidentiality, separation of identifiers and data). Include information on any measures that will be taken during storage, access, use, and transmission of study data.

If you will obtain information on participants' substance use disorder from a treatment provider, then only answer this question for all other data not related to substance use records (e.g., self-report data). All confidentiality and data security questions around substance use records should be recorded in [Appendix J](#).

- Data collected in the study will be kept strictly confidential and will not be shared with anyone outside of the research team. All research specific materials will be coded with a research number to de-identify the data and will contain no other identifying information to protect participant confidentiality.

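### Staff who may know past assignments are allowed to make pre-randomisation calls, and the block unit is ambiguous: a minor selection risk that is cheap to remove

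*Protocol*

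**What the plan says.** **Who calls.** Protocol section 3.2 says of the confirmation calls: "These calls will be completed by study staff, including the research assistant, senior project manager, and intervention staff, if needed". Section 4.1 describes the same step as "passing a consent quiz during the confirmation call by study staff (research assistant"), with no mention of intervention staff. Sections 6.2 and 6.3 refer only to a study staff person.

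**Contact between call and randomisation.** If the locator form or baseline survey is not finished, section 3.2 says "study staff will reach out to the participants to encourage them to complete these required activities". Enrollment must be complete within one week, and randomisation follows the baseline survey.

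**The block rule.** Section 3.2: "We will use block randomization to assign a group of three participants to each condition". The stated purpose includes "to allow us to equal number of people in each group throughout the study recruitment period".

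**Who learns the assignments.** Section 8.1: "WTV will be responsible for contacting enrolled participants to inform them of their random assignment". Section 3.2 says the same. The program table in section 4.1 places the coaches with WTV ("Weekly sessions are in a small group with WTV coach and 3 to 8 study participants using Zoom"), and sections 6.2 and 9.9 also treat the coaches and the clinical team as WTV's. Section 3.2 further implies a running count for one arm: "When Program A reaches approximately nine participants, we will form the next group assigned to Program A".

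**The concern.** The two sections differ on who may speak to a participant before randomisation, and the broader one admits people from the side of the trial that treats participants. Their organisation is told who was assigned to what. If such a caller can partly foresee the next assignment, the effort put into an enrollment may depend on the arm expected. The discretionary steps are the consent review after a failed quiz, the answering of questions, and reminders to finish the baseline survey.

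The trial is open, the primary outcome is the CSO's own report of treatment entry, and the arms are small (84 / 3 = 28 each if equal). A few selectively completed enrollments could make the arms differ before treatment starts.

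The block sentence adds to this, because its unit is unclear and each reading leaves the next assignment partly predictable from earlier ones.

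**Working it through.** The protocol gives no predictability figure to reproduce, so I computed the ceilings.

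**Inputs.** Three arms, equal allocation, up to 84 participants (sections 3.1 and 3.2). The observer knows every earlier assignment and guesses the arm with most places left in the block. Without blocking, the guess is right 1/3 = 33% of the time.

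**Blocks of three (one per arm).** The chance of a correct guess at slots 1, 2 and 3 is 1/3, 1/2 and 1.
- Mean: (1/3 + 1/2 + 1)/3 = 11/18 = 61%.
- Slots known with certainty: 1 in 3, or 28 of 84.

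**Blocks of nine (three per arm).** The chance at each slot is the expected value of (most places left in any arm) / (places left in the block). Exact enumeration gives 1/3, 3/8, 3/7, 25/56, 33/70, 15/28, 4/7, 5/8 and 1.
- The sum is 4021/840, so the mean is 4021/7560 = 53%.
- Slots known with certainty: chance 1/28, 1/4 and 1 at slots 7, 8 and 9, so (1/28 + 1/4 + 1)/9 = 1/7 = 14%, about 12 of 84.

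For these two readings the observer need not know the block size, because guessing the arm with the fewest participants so far gives the same 61% and 53%. Current counts for all three arms are needed.

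**Effect of delay.** The caller acts before the survey is submitted, so other people may be randomised first. If the target falls into a later block, the guess drops to 1/3.

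| Others randomised first | Blocks of three: best guess (certain) | Blocks of nine: best guess (certain) |
|---|---|---|
| 0 | 61% (33%) | 53% (14%) |
| 1 | 39% (0%) | 46% (3%) |
| 2 | 33% (0%) | 43% (0.4%) |

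For example, with blocks of three and one person in between: (1/3 + 1/2 + 1/3)/3 = 7/18 = 39%.

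**Illustration at the time of the call.** The protocol gives no accrual rate. I assumed 84 people over 19.6 weeks (15 November 2019, the DSMB review date in section 9.10, to 31 March 2020 in section 3.2), which is 4.3 a week. As a faster case I assumed 84 over 8 weeks, or 10.5 a week. The number randomised in between is taken as Poisson.

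| Survey returned after | Blocks of three | Blocks of nine |
|---|---|---|
| 1 day | 41–50% | 45–49% |
| 3 days | 34–39% | 38–44% |
| 7 days | 33–34% | 34–38% |

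Neither start date nor duration is stated as such in the protocol, so these ranges show only the direction and rough speed of the decline.

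**The case against.** **The staffing conflict is modest.** Section 3.2 is the detailed procedure and treats intervention staff as back-up. Section 4.1 is a summary that does not exclude others. That stands, but section 3.2 still expressly permits the overlap.

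**Foreknowledge is inferred.** A reader might conclude that WTV callers see each assignment as it is made. The text does not support this. Section 8.1 has an enrollment spreadsheet sent to WTV without saying how often, no passage says an individual coach sees it, and the only running count described is for Program A. That coaches are the intervention staff meant in section 3.2 is itself an inference, though a strong one. This objection stands, and it is why the percentages are ceilings.

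**The safeguards are real.** Screening is automated, anonymous and unlinked to later data. Consent precedes the call, the quiz has a fixed pass mark, and the baseline survey is self-administered. Follow-up of incomplete data is limited to two contacts, and PHMC runs data collection. The protocol hands the caller no prognostic data. The route to bias is therefore narrow.

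**Two stronger readings are tempting.** One is that allocation is unconcealed. The protocol does not say so: a designated person computes the assignment, and list handling may be described in a document not shown. The other is to quote the runs-of-three reading, where the ceiling is (1/3 + 1 + 1 + 1/2 + 1 + 1 + 1 + 1 + 1)/9 = 87%. That is the least natural meaning of block randomisation, and it needs the added assumption that runs are balanced within nine to meet the equal-numbers aim. It shows why the sentence needs clarifying, but it does not measure the risk.

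**Conclusion.** The point holds as a low-severity, cheap improvement. Sections 3.2 and 4.1 should agree on who makes pre-randomisation calls, and the block sentence should have one meaning. The ceilings of 61% and 53% against 33% assume a caller with current counts for all three arms and nobody randomised in between. With one other person first they are 39% and 46%; with two, 33% and 43%. Usable foreknowledge under the block readings is therefore small unless the survey comes back quickly. Reminders sent later in the enrollment week sit closer to the assignment than the call does, so they belong in the fix. Nothing in the protocol shows that bias would in fact occur.

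The figure of 28 per arm is not a guaranteed maximum: with blocks of nine, 84 = 9 × 9 + 3, so an arm could reach 27 + 3 = 30.

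**What to change.** 1. **Separate the roles (the essential step).** In section 3.2, remove intervention staff from the list of callers so that it agrees with section 4.1. State that confirmation calls, the consent quiz, consent review and enrollment reminders are done only by existing research staff who do not deliver the programs and do not see the running assignments. The senior project manager can remain as back-up on the same condition. Keep the data flow in sections 8.1 to 8.3, except that callers do not handle the assignment file.

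2. **Clarify the block rule.** Replace the sentence in section 3.2 with wording such as: *Participants are individually randomised 1:1:1 in permuted blocks. Block sizes and the unreleased list are withheld from anyone who recruits, calls or treats participants.* Keep the rule that assignment follows the baseline survey.

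Varying the block sizes is optional and does not replace step 1. With sizes of 3, 6 and 9 drawn at random, as an illustration, simulation puts certain slots at about 4%, but the best guess stays at about 55%. That is no lower than the 53% for fixed blocks of nine.

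**Cost.** A few lines of protocol text and a new allocation list. There are fewer people to cover calls within the one-business-day goal; the protocol gives no staffing numbers, so whether this strains the team cannot be judged from it. Arms may be slightly uneven at any moment (by up to three with blocks of nine), which could slightly delay filling a Program A group.
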